### 8.2 Safety and Other Assessments

Safety will be assessed at each stage of the study by the RA and RN using the health assessments checklist. There will be ongoing review by the PI and study physician with positive findings of a change in symptom or single severe symptom triggering clinical referral to treating physician or ED. The RA will ensure that the enrolled study subjects are eligible and sign informed consent. The study RN will be present with the study subject during all procedures, and the study subject's vital signs (HR, BP) will be measured by continuous monitoring. Any adverse events will be documented as described below.

### 8.3 Adverse Events and Serious Adverse Events

#### 8.3.1 Definition of Adverse Events (AE)

Adverse event means any untoward medical occurrence associated with the use of an intervention in humans, whether or not considered intervention-related (21 CFR 312.32 (a)).

### **8.3.2 Definition of Serious Adverse Events (SAE)**

An adverse event (AE) or suspected adverse reaction is considered "serious" if, in the view of either the investigator or sponsor, it results in any of the following outcomes: death, a life-threatening adverse event, inpatient hospitalization or prolongation of existing hospitalization, a persistent or significant incapacity or substantial disruption of the ability to conduct normal life functions, or a congenital anomaly/birth defect. Important medical events that may not result in death, be life-threatening, or require hospitalization may be considered serious when, based upon appropriate medical judgment, they may jeopardize the participant and may require medical or surgical intervention to prevent one of the outcomes listed in this definition.

Examples of such medical events include allergic bronchospasm requiring intensive treatment in an emergency room or at home, blood dyscrasias or convulsions that do not result in inpatient hospitalization, or the development of drug dependency or drug abuse.

### **8.3.3 Classification of an Adverse Event**

#### **8.3.3.1 Severity of Event**

For adverse events (AEs) not included in the protocol defined grading system, the following guidelines will be used to describe severity.

- **Mild** — Events require minimal or no treatment and do not interfere with the participant's daily activities.
- **Moderate** — Events result in a low level of inconvenience or concern with the therapeutic measures. Moderate events may cause some interference with functioning.
- **Severe** — Events interrupt a participant's usual daily activity and may require systemic drug therapy or other treatment. Severe events are usually potentially life-threatening or incapacitating. Of note, the term "severe" does not necessarily equate to "serious".

#### **8.3.3.2 Relationship to Study Intervention**

All adverse events (AEs) must have their relationship to study intervention assessed by the clinician who examines and evaluates the participant based on temporal relationship and his/her clinical judgment. The degree of certainty about causality will be graded using the categories below. In a clinical trial, the study product must always be suspect.

- **Related** — The AE is known to occur with the study intervention, there is a reasonable possibility that the study intervention caused the AE, or there is a temporal relationship between the study intervention and event. Reasonable possibility means that there is evidence to suggest a causal relationship between the study intervention and the AE.

- **Not Related** — There is not a reasonable possibility that the administration of the study intervention caused the event, there is no temporal relationship between the study intervention and event onset, or an alternate etiology has been established.

OR

- **Definitely Related** — There is clear evidence to suggest a causal relationship, and other possible contributing factors can be ruled out. The clinical event, including an abnormal laboratory test result, occurs in a plausible time relationship to study intervention administration and cannot be explained by concurrent disease or other drugs or chemicals. The response to withdrawal of the study intervention (dechallenge) should be clinically plausible. The event must be pharmacologically or phenomenologically definitive, with use of a satisfactory rechallenge procedure if necessary.
- **Probably Related** — There is evidence to suggest a causal relationship, and the influence of other factors is unlikely. The clinical event, including an abnormal laboratory test result, occurs within a reasonable time after administration of the study intervention, is unlikely to be attributed to concurrent disease or other drugs or chemicals, and follows a clinically reasonable response on withdrawal (dechallenge). Rechallenge information is not required to fulfill this definition.
- **Potentially Related** — There is some evidence to suggest a causal relationship (e.g., the event occurred within a reasonable time after administration of the trial medication). However, other factors may have contributed to the event (e.g., the participant's clinical condition, other concomitant events). Although an AE may rate only as "possibly related" soon after discovery, it can be flagged as requiring more information and later be upgraded to "probably related" or "definitely related", as appropriate.
- **Unlikely to be related** — A clinical event, including an abnormal laboratory test result, whose temporal relationship to study intervention administration makes a causal relationship improbable (e.g., the event did not occur within a reasonable time after administration of the study intervention) and in which other drugs or chemicals or underlying disease provides plausible explanations (e.g., the participant's clinical condition, other concomitant treatments).
- **Not Related** — The AE is completely independent of study intervention administration, and/or evidence exists that the event is definitely related to another etiology. There must be an alternative, definitive etiology documented by the clinician.

### 8.3.3.3 Expectedness

The PI and study team will be responsible for determining whether an adverse event (AE) is expected or unexpected. An AE will be considered unexpected if the nature, severity, or

frequency of the event is not consistent with the risk information previously described for the study intervention.

#### **8.3.4 Time Period and Frequency for Event Assessment and Follow-Up**

The occurrence of an adverse event (AE) or serious adverse event (SAE) may come to the attention of study personnel during study visits and interviews of a study participant presenting for medical care, or upon review by a study monitor.

All AEs including local and systemic reactions not meeting the criteria for SAEs will be captured on the appropriate case report form (CRF). Information to be collected includes event description, time of onset, clinician's assessment of severity, relationship to study product (assessed only by those with the training and authority to make a diagnosis), and time of resolution/stabilization of the event. All AEs occurring while on study must be documented appropriately regardless of relationship. All AEs will be followed to adequate resolution.

Any medical condition that is present at the time that the participant is screened will be considered as baseline and not reported as an AE. However, if the study participant's condition deteriorates at any time during the study, it will be recorded as an AE.

Changes in the severity of an AE will be documented to allow an assessment of the duration of the event at each level of severity to be performed. AEs characterized as intermittent require documentation of onset and duration of each episode.

The PI, study coordinator, or research assistant will record all reportable events with start dates occurring any time after informed consent is obtained until 7 (for non-serious AEs) or 30 days (for SAEs) after the last day of study participation. At each study visit, the investigator will inquire about the occurrence of AE/SAEs since the last visit. Events will be followed for outcome information until resolution or stabilization.

#### **8.3.5 Adverse Event Reporting**

##### **Plan for reporting UPIRSOs (including Adverse Events) to the IRB**

The principal investigator will report the following types of events to the IRB: Any incident, experience or outcome that meets ALL 3 of the following criteria:

1. Is unexpected (in terms of nature, specificity, severity, or frequency) given (a) the research procedures described in the protocol-related documents, such as the IRB-approved protocol and informed consent document and (b) the characteristics of the subject population being studied; AND
2. Is related or possibly related to participation in the research (possibly related means there is a reasonable possibility that the incident, experience, or outcome may have been caused by the procedures involved in the research); AND

3. Suggests that the research places subjects or others at greater risk of harm (including physical, psychological, economic, legal, or social harm) than was previously known or recognized.

Unanticipated Problems Involving Risks to Subjects or Others (UPIRSOs) may be medical or non-medical in nature, and include — but are not limited to — serious, unexpected, and related adverse events and unanticipated adverse device effects. These UPIRSOs/SAEs will be reported to the IRB in accordance with Yale IRB Policy 710, using the appropriate forms found on the website. All related events involving risk but not meeting the prompt reporting requirements described in IRB Policy 710 should be reported to the IRB in summary form at the time of continuing review. If appropriate, such summary may be a simple brief statement that events have occurred at the expected frequency and level of severity as previously documented. In lieu of a summary of external events, a current DSMB report can be submitted for research studies that are subject to oversight by a DSMB (or other monitoring entity that is monitoring the study on behalf of an industry sponsor).

### **8.3.6 Serious Adverse Event Reporting**

The study clinician will immediately report to the sponsor any serious adverse event, whether or not considered study intervention related, including those listed in the protocol or investigator brochure and must include an assessment of whether there is a reasonable possibility that the study intervention caused the event. Study endpoints that are serious adverse events (e.g., all-cause mortality) must be reported in accordance with the protocol unless there is evidence suggesting a causal relationship between the study intervention and the event (e.g., death from anaphylaxis). In that case, the investigator must immediately report the event to the sponsor.

All serious adverse events (SAEs) will be followed until satisfactory resolution or until the site investigator deems the event to be chronic or the participant is stable. Other supporting documentation of the event may be requested by the Data Coordinating Center (DCC)/study sponsor and should be provided as soon as possible.

The study sponsor will be responsible for notifying the Food and Drug Administration (FDA) of any unexpected fatal or life-threatening suspected adverse reaction as soon as possible, but in no case later than 7 calendar days after the sponsor's initial receipt of the information. In addition, the sponsor must notify FDA and all participating investigators in an Investigational New Drug (IND) safety report of potential serious risks, from clinical trials or any other source, as soon as possible, but in no case later than 15 calendar days after the sponsor determines that the information qualifies for reporting.

### **8.3.7 Reporting Events to Participants**

Not applicable.

**8.3.8 Events of Special Interest**

Not applicable.

**8.3.9 Reporting of Pregnancy (if applicable)**

Pregnancy status will be directly communicated verbally to all study subjects who receive a pregnancy test prior to study procedures.

**8.4 Unanticipated Problems****8.4.2 Unanticipated Problem Reporting**

The investigator will report unanticipated problems (UPs) to the reviewing Institutional Review Board (IRB) and to the Data Coordinating Center (DCC)/lead principal investigator (PI). The UP report will include the following information:

- Protocol identifying information: protocol title and number, PI's name, and the IRB project number;
- A detailed description of the event, incident, experience, or outcome;
- An explanation of the basis for determining that the event, incident, experience, or outcome represents an UP;
- A description of any changes to the protocol or other corrective actions that have been taken or are proposed in response to the UP.

To satisfy the requirement for prompt reporting, UPs will be reported using the following timeline:

UPs will be promptly reported to the IRB within 5 business days and to the DCC/study sponsor in accordance with policy and regulatory requirements.

**8.4.3 Reporting Unanticipated Problems to Participants**

Participants will be individually informed about unanticipated problems.

# 9 - Statistical Considerations

## 9.1 Statistical Hypotheses

We hypothesize that computed nicotine flux will predict the rate of nicotine rise and maximum nicotine concentration observed in arterial blood, and that protonated nicotine will result in higher delivery.

## 9.2 Sample Size Considerations

Assuming an alpha level of 0.05 and an ICC of 0.4 (which conservatively assumes only modest correlation between Cmax measures within the same participant), we estimated that we would need a total sample size of 15 subjects (completing two sessions) to detect with 90% power a medium effect size of 0.4. In the event of participant attrition, we will recruit additional participants to replace those lost to follow up and maintain statistical power. With an anticipated higher ICC and a higher relationship between flux and Cmax, as suggested by our prior work, this design will be well-powered to investigate the relationship of Cmax and flux concentrations for each form separately, and over 88% power to detect an effect size 0.4 for the between and within group comparisons [i.e., form\*concentration]. We will continue recruitment until we achieve the targeted sample size.

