### **6.3 Measures to Minimize Bias: Randomization and Blinding**

The flux/form conditions will be tested by participants in two lab visits separated by one to four weeks to minimize carryover effects. All sessions will be double-blinded. In the first visit, participants will use the ENDS device with one nicotine form and four fluxes in random order. Participants will be instructed to attend the lab for a second visit, to test the four fluxes but with the other nicotine form (free base or protonated). The second visit will allow us to isolate the effect of nicotine form on nicotine delivery. The order of nicotine form in the two visits will be counter-balanced across participants.

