## 9.4 Statistical Analyses

To account for the repeated Cmax (adjusted for baseline at time zero) assessments design and to evaluate the extent of within-subject correlation of Cmax outcomes, we will first compute using linear mixed effect models, the intra-class correlation coefficients for the Cmax measures, first separately for each of the forms (protonated and free base) and then for all Cmax measurements from the same participant. This step will help us understand the magnitude within-subject correlation of Cmax measures and to compare the within-subject correlation for the two main forms. Next, for each of the forms, we will investigate how Cmax relates to changing nicotine flux, by using linear mixed effect models (accounting for the within-subject design) and flux conditions as a predictor; we will investigate flux conditions both categorically and continuously to detect whether the change in Cmax follows a specific linear trend or whether some flux concentrations relate differently to Cmax. We will use model fit criteria to select the correlation structure and representation of flux concentrations that best describes the data. This investigation will be complemented by splines and locally weighted scatterplot smoothing (LOWESS) graphs to visualize plots of Cmax changes over the flux values. These analyses will be performed separately for the protonated and freebase conditions to assess similarities and differences in how the form of nicotine is influencing the Cmax-flux concentration relationship. Finally, we will integrate the form effect by using linear mixed models with both concentration and form as predictors as well as an interaction term between form\*concentration

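### Do the power figures in section 9.2 (90% for a medium effect of 0.4, over 88% for form by concentration) misstate what 15 participants can detect?

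*Combined protocol and SAP*

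**What the plan says.** Section 9.2 (Sample Size Considerations) starts from "Assuming an alpha level of 0.05 and an ICC of 0.4", describes that ICC as conservative, and concludes that "we would need a total sample size of 15 subjects (completing two sessions) to detect with 90% power a medium effect size of 0.4". A conditional statement follows. It opens "With an anticipated higher ICC and a higher relationship between flux and Cmax, as suggested by our prior work" and says that the design will then be well powered to study flux and Cmax within each form. The same sentence adds "over 88% power to detect an effect size 0.4 for the between and within group comparisons [i.e., form", where the bracket goes on to name the form-by-concentration interaction. Participants lost to follow-up are replaced, so no dropout allowance is made.

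The design is a 4 x 2 crossover (section 4.1). Every participant takes all four fluxes in each of two visits, one visit per form, and section 6.3 adds that "The order of nicotine form in the two visits will be counter-balanced across participants". In section 9.4 the flux analyses are run separately by form, where "we will investigate flux conditions both categorically and continuously to detect whether the change in Cmax follows a specific linear trend". A joint model with form, concentration and their interaction comes last.

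**The concern.** Two features invite suspicion.

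First, the plan gives 0.4 no metric. The calculation that fits the design and returns both 15 participants and 90% takes 0.4 as Cohen's f for the four fluxes within one form. On the usual scale for f (0.25 medium, 0.40 large) the adjective in section 9.2 would then be wrong. A reader could believe that the trial has 90% power for a medium flux effect when the single-form omnibus test has about half that, and could read a null single-form result as evidence against a flux effect.

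Second, the interaction power is described as a comparison between and within groups, yet the trial has no between-participant groups. The figure is close to what a two-group mixed design with 7 per group would give, which suggests that the wrong design was entered in the software.

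**Working it through.** **Inputs from the documents.** Alpha 0.05, ICC 0.4, effect size 0.4 and N = 15 (section 9.2); four fluxes of 9, 18, 27 and 35 µg/sec and two forms, all within participant (section 4.1).

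**Assumptions.** The effect size is Cohen's f, the test is a repeated-measures F test, and correlation is exchangeable. Power comes from the noncentral F distribution with λ = f² × N × m / (1 − ICC), where m is the number of measures per participant.

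**Step 1: the 90% figure.** One form, m = 4, df = 3 and 3(N − 1).

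- N = 15: λ = 0.16 × 15 × 4 / 0.6 = 16, df 3 and 42, power 90.8%.
- N = 14: λ = 0.16 × 14 × 4 / 0.6 = 14.93, df 3 and 39, power 88.4%.

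Fifteen is the smallest N that reaches 90%, as the plan states. Cohen's d = 0.4 does not reproduce it: 26% for a two-sided paired comparison of single bouts, 75% for means of four bouts.

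**Step 2: a smaller effect.** With f = 0.25, N = 15 and ICC 0.4:

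| Test | λ | df | Power |
|---|---|---|---|
| One form, omnibus | 0.0625 × 60 / 0.6 = 6.25 | 3, 42 | 49.5% |
| One form, linear trend | 6.25 | 1, 42 | 68.5% |
| Both forms, omnibus | 0.0625 × 120 / 0.6 = 12.5 | 3, 42 to 3, 98 | 81.9% to 84.1% |
| Both forms, linear trend | 12.5 | 1, 42 to 1, 98 | 93.2% to 93.8% |

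At ICC 0.6 the one-form omnibus test has 68.6%. The 49.5% therefore combines an effect smaller than the plan's target, an ICC the plan calls conservative, and the least favourable of these flux tests.

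**Step 3: is f = 0.25 a natural target here?** The four fluxes have mean 22.25 and SD 9.73. If f = 0.40 and Cmax is linear in flux, the difference between 9 and 35 µg/sec is 0.40 × 26 / 9.73 = 1.07 SD. If baseline-corrected Cmax is also proportional to flux (an assumption), then f = (9.73 / 22.25) / CV = 0.437 / CV, where CV is the SD within a flux condition divided by mean Cmax. So f falls below 0.40 only when CV exceeds 0.437 / 0.40 = 109%, and reaches 0.25 only at 0.437 / 0.25 = 175%. The documents give no CV, but they offer no reason to centre the design on f = 0.25 either.

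**Step 4: the interaction figure.** Form and flux are both within participant, so m = 8. The answer depends on how the 0.4 is scaled.

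- f = 0.40 over the eight cells: λ = 0.16 × 120 / 0.6 = 32, power 99.8% (df 3, 42) to 99.9% (df 3, 98).
- f = 0.40 for flux in one form and no flux effect in the other: the interaction f over eight cells is half of 0.40, that is 0.20. λ = 0.04 × 120 / 0.6 = 8, power 60.9% (df 3, 42) to 63.5% (df 3, 98).
- f = 0.40 relative to the SD of the between-form difference: λ = 0.16 × 60 = 9.6, df 3 and 42, power 69.7%.
- For comparison, a two-group mixed design: 88.1% at N = 14 and 90.6% at N = 15.

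The plan's figure is a lower bound. The first crossover definition meets it and the next two do not. The two-group calculation at N = 15 also meets it.

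**The case for a change.** The strongest case for a correction is that a sample-size paragraph should tell the reader what the trial can detect, and this one does not. Power for the interaction runs from 61% to 99.8% depending on a definition that is left out, and the wording about groups does not describe a crossover. The single-form analysis is central to section 9.4, and a null result there could be over-read. The expected higher ICC is not quantified, and an f of 0.25 would need an ICC of about 0.76 to reach 90% in the single-form omnibus test. One reworded paragraph would settle all of this.

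Most of that stands as a comment on reporting. It does not show a wrong figure. The numerical target of 0.4 is disclosed and the 90% follows from it. The complaint about the adjective needs a metric inferred from the result and then a benchmark brought in from outside. The sentence about each form separately depends on a higher ICC and a stronger flux relationship; it does not promise 90% for a medium effect at ICC 0.4. For the interaction, the plan can be shown neither to understate nor to overstate. Replacing the bound with 99.8%, without defining the effect, could mislead more than the present text. That the figure came from a 7-per-group calculation is only a guess.

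**Conclusion.** No change to the plan follows. The 15 participants and 90% power agree with each other (90.8% at 15, 88.4% at 14), provided that 0.4 is Cohen's f for flux within one form, ICC is 0.4 and correlation is exchangeable. The interaction statement is a lower bound that holds on one reasonable definition (99.8%) and fails on others (61% to 70%); the document does not say which was used.

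The gap is an unnamed metric, test and contrast, one loose adjective, and group wording carried into a within-participant design. Filling it would alter no sample size, endpoint or analysis. The estimates come from the mixed models of section 9.4, which treat flux as categorical and as continuous, by form and then jointly. Anyone judging a null single-form result will have the observed effect and its precision, which are better guides than the planning figure. If section 9.2 is reworded for other reasons, the metric and the definition of the interaction effect could be named then.
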